9.6. Post-Placement Antiplatelet Agents

The subject should be tested for antiplatelet response per standard of care and the appropriate dose of antiplatelet agents will be given after the Pipeline[™] Vantage Device implant procedure as defined below.

- Aspirin: At least 81 mg daily for a minimum of 6 months
- **P2Y₁₂ Platelet Inhibitor:** Daily for a minimum of 3 months. Only the following agents shall be utilized:

Clopidogrel: At least 75 mg daily for a minimum of 3 months

In situations where patients are hypo-responders to Clopidogrel:

• **Prasugrel** (Only for subjects <75 years of age and should not be used in subjects with a history of TIA or stroke): 5-10 mg once daily for a minimum of 3 months

Page 81 of 144

- Or
- **Ticagrelor:** 60-90 mg twice daily with a maximum daily dose of Aspirin not exceeding 100 mg for a minimum of 3 months

Note: Treating physicians should evaluate extending the DAPT regimen based on individual subject condition and response (per their standard of care) Dosing amount will be collected on eCRFs.

9.7. Discharge Exam

At day 7 or discharge (whichever is earlier), the following study assessments shall be performed:

- Record protocol specified medications
- Record concomitant medications
- mRS to be carried out by a certified independent assessor at site
- Full neurological exam and assessment of aneurysm symptoms (new, worsened, improved, stable)

Medtronic Controlled Information

• Assessment of Adverse events

Subject discharge disposition will be documented in the eCRFs.

PR-NV16099

Version C

9.8. Retreatment

At the Investigator's discretion, the target aneurysm may be retreated at any time during the study. The retreatment procedure can include any endovascular or surgical intervention including the implant of the Pipeline[™] Vantage Device. In such situations, the date that the subject receives the initial Pipeline[™] Vantage Device implant (and not the date of the retreatment) will be considered Day 0.

Reason(s) for retreatment of aneurysm shall be documented:

- Device Movement
 - Foreshortening (Peri-procedural or Delayed)
 - Migration
- Aneurysm Growth
- Aneurysm Rupture
- Aneurysm Non-Occlusion
- Insufficient Neck Coverage

Type of Retreatment will be documented:

- Planned
- Unplanned

A retreatment will be considered an "Unscheduled Visit" and subjects will be required to undergo the following study assessments:

- Full neurological exam and assessment of aneurysm symptoms (new, worsened, improved, stable)
- Record concomitant and protocol-specified medications
- Imaging (per standard of care)
- NIHSS
- mRS assessment to be carried out by a certified independent assessor at site
- Assessment of Adverse events

		· · · · · · · · · · · · · · · · · · ·	and the second sec
PR-NV16099	Version C	Page 83 of 144	Medtronic

Data will be collected for all retreatment procedures in the Retreatment eCRFs. Retreatments should be reported as an SAE.

9.9. Follow-up Evaluations

Subjects that consented/enrolled and underwent a successful Pipeline[™] Vantage Device implant will undergo in-clinic follow-up at 30 days, 180 days, 1 year, 2 years, and 3 years. Subjects that had a Pipeline[™] Vantage device attempt but were not successfully implanted with the Pipeline[™] Vantage device at the index procedure or subsequent attempts, will undergo in-clinic follow-up at 1 year.

9.9.1. 30-Day

At day 30 post-procedure (±7 days), the following study assessments shall be performed and recorded in the eCRFs:

- Record protocol specified medications
- Record concomitant medications
- mRS assessment to be carried out by a certified independent assessor at site
- Full Neurological Exam and assessment of aneurysm symptoms (new, improved, worsened, stable)
- Assessment of Adverse events of interest

9.9.2. 180-Day

At day 180 post-procedure (± 30 days), the following study assessments shall be performed and recorded in the eCRFs:

- Record protocol specified medications
- Record concomitant medications
- DSA imaging, if done per standard of care; if DSA not performed per standard of care, subject must undergo CTA imaging.
- mRS assessment to be carried out by a certified independent assessor at site
- Full neurological exam and assessment of aneurysm symptoms (new, worsened, improved, stable)
- Assessment of Adverse events of interest

PR-NV16099

Version C

9.9.3. 1-Year

At 1-year post-procedure (±56 days), the following study assessments shall be performed and recorded in the eCRFs:

- Pregnancy test (Pregnancy test (serum or urine) only required for females of childbearing potential. Females who are surgically sterile or post-menopausal are not required to take a pregnancy test)
- Record protocol specified medications
- Record concomitant medications
- DSA imaging
- mRS assessment to be carried out by a certified independent assessor at site
- Full neurological exam and assessment of aneurysm symptoms (new, worsened, improved, stable)
- NIHSS
- Assessment of Adverse events of interest

9.9.4. 2-Year

At 2-year post-procedure (±56 days), the following study assessments shall be performed and recorded in the eCRFs:

- Pregnancy test (Pregnancy test (serum or urine) only required for females of childbearing potential. Females who are surgically sterile or post-menopausal are not required to take a pregnancy test). At the 2-year follow-up, pregnancy test is only required for female subjects of childbearing potential that are undergoing DSA imaging.
- Record protocol specified medications
- Record concomitant medications
- If aneurysm is not occluded at 1 year or subsequent follow-up visits (per core lab assessment), DSA must be performed at 2-year follow-up. If child bearing potential woman becomes pregnant during the study, subject may obtain MRA without contrast instead of DSA.
- mRS assessment to be carried out by a certified independent assessor at site

ADVANCE Clinica	I Investigation Plan		
PR-NV16099	Version C	Page 85 of 144	Medtronic

- Full neurological exam and assessment of aneurysm symptoms (new, worsened, improved, stable)
- Assessment of Adverse events of interest

9.9.5. 3-Year

At 3-year post-procedure (±56 days), the following study assessments shall be performed and recorded in the eCRFs:

- Pregnancy test (Pregnancy test (serum or urine) only required for females of childbearing potential. Females who are surgically sterile or post-menopausal are not required to take a pregnancy test). At the 3-year follow-up, pregnancy test is only required for female subjects of childbearing potential that are undergoing DSA imaging.
- Record protocol specified medications
- Record concomitant medications
- If aneurysm is not occluded at 1 year and subsequent follow-up visits (per core lab assessment), DSA must be performed at 3- year follow-up. Subjects with aneurysm occluded at 1 year and subsequent follow-up visits (per core lab assessment) to undergo DSA, if performed per standard of care; if DSA not collected per standard of care, subject must undergo CTA imaging. Under certain conditions, MRA imaging may be obtained instead of a DSA or CTA imaging e.g., subjects with iodine allergies, borderline renal function, pregnancy, or concerns over excessive radiation. The justification for using MRA over DSA or CTA should be captured in the case report form. Precaution: DSA or CTA imaging are preferred over MRA imaging due to the risk of reduced image quality (artifact) when attempting to visualize near or inside the implanted device with MRA imaging.
- mRS assessment to be carried out by a certified independent assessor at site
- Full neurological exam and assessment of aneurysm symptoms (new, worsened, improved, stable)
- Assessment of Adverse events of interest

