9.2. Baseline

The baseline visit must occur 7 to 30 days prior to the procedure day.

During baseline, the following assessments should be completed.

- Inclusion/exclusion criteria assessment
- Informed consent
- Demographics: age, gender, ethnicity and race
- Medical and surgical history
- Risk factors, including aneurysm history; note that risk factors to be collected for all enrolled subjects regardless of the aneurysm size
- Platelet count and WBC (can be done any time prior to index procedure)
- Coagulation Profile (can be done any time prior to index procedure)
- Protocol specified Medications
- Record concomitant medications
- DSA, CTA or MRA imaging (The baseline DSA, CTA or MRA images must be taken no more than 90 calendar days prior to the procedure)
- Neurological Exam
- Assessment of Adverse Events (Assess adverse events after informed consent is signed)

This data will be collected in the electronic case report forms (eCRF) for all subjects enrolled and treated in the study. The de-identified images will be sent to the Core Lab for review. Enrolled subjects determined to be ineligible for the study prior to the puncture at the arterial access site on the day of the study procedure (Day 0), will only require the reason for the eligibility failure and study exit to be recorded in the eCRF. No further eCRFs are required.

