10.1. Potential Risks

Residual risks from the risk management workbook (RMW15-0012_L) for Pipeline[™] Vantage was analyzed to determine the potential clinical harms that may be associated with the use of the Pipeline[™] Vantage device. Residual risks, as identified in the risk management work (RMW15-0012_L) are included in the below potential risks. Note that the Risk Management Workbook is a document that is continuously updated. The most current associated risks are also captured in the Instructions For Use (IFU), (P/N M993912ADOC2). Anticipated Adverse Events and Adverse Device Effects associated with use of the study device and the study procedure(s) include:

Neurological Events of Interest	An event of interest related to the target aneurysm clinical outcome and includes the following events of interest:
	Death
	Neurological Death
	Stroke*
	Major
	Minor
	ICH*
	Target Aneurysm Rupture
	Transient Ischemic Attack
	Cerebral Infarction
	Symptomatic
	Asymptomatic
	Target Aneurysm Retreatment
	Planned
	Unplanned
	Neurological Deficit (decline in mRS)*
	Focal
	Generalized
	Visual Symptoms*:
	Scintillations
	Blurred vision
	Floaters
	Diplopia
	Retinal Artery Occlusion
	Amaurosis Fugax
	Vision Loss
	Visual Field Deficit
	*Ipsilateral Territory: Presumed to be of the vascular origin of the treated vascular
	territory

Medtronic Controlled Information

PR-NV16099	Version C	Page 90 of 144	Medtronic
Procedural Events of Interest	Events representing the endovascular p treatment. Complications could be fatal Delayed. These include:		
	Access Site Complications:		
	Hematoma/hemorrhage Retroperitoneal Localized Pseudoaneurysm (PSA) Vessel occlusion Arteriovenous fistula (AVF) Deep Vein Thrombosis (DVT) Local neurogenic or nerve complica Pain Vascular Complications (Intra-Cranial o Dissection Perforation Rupture Vasospasms (vasoconstriction) Intracranial fistula formation Occlusion Thromboembolic Complications Distal Thromboembolic complii Anesthesia related complications Aspiration	r Extra Cranial):	
	Hypertension		
	Hypotension		
	Contrast Related Complications: Burning Sensation Nausea Contrast Nephropathy Visual Impairment/Visual symptom	ſS	
	Excessive Radiation Complications: Skin reddening, Blisters and ulcers,		
	Hair loss (alopecia) Cataracts		
	Late appearing cancers Systemic complications: Infection, Shoc	k, Arrhythmia	

PR-NV16099	Version C	Page 91 of 144	Medtronic

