Medtronic

11. Adverse Events and Device Deficiencies

All adverse events (AEs) will be collected and evaluated from point of enrollment through study exit per the Schedule of Assessments for all subjects enrolled in the study. Adverse event status will be evaluated throughout the study.

Investigators must obtain all information available to determine the causality, seriousness and outcome of the AE and to assess whether it meets the criteria for expedited reporting requiring notification to the Sponsor, and where applicable, regulatory agency(ies) and IRBs/REBs/Ethics Committees within the specified reporting timeframe per 21 CFR 812 or local regulations. Reported AEs shall be categorized by the site investigator when reporting to the sponsor using the definitions provided in **Section 11.1 and 11.3**.

Target Aneurysm related signs and symptoms that in the opinion of the Investigator existed prior to the point of puncture at the arterial access site on the day of the study procedure (Day 0) are not considered AEs (but will be collected as Medical History/ Risk Factors) unless the condition recurs after the subject has recovered from the pre-existing condition, or the condition worsens in severity, seriousness or frequency during the study.

If the subject is enrolled and undergoes puncture at the arterial access site but an attempt to deploy the Pipeline[™] Vantage Device is not made due to ineligibility of the subject for the study (e.g., inability to access the aneurysm or other exclusion criterion identified during the procedure) any adverse events or device deficiencies that occur are to be collected through subject's study exit.

All AEs, as well as their start dates, action taken, severity, causality assessment, seriousness and outcome should be documented in the subject's medical records and in the eCRF.

A list of foreseeable adverse events of the study is provided in **Section 10.1**.

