13.8.4. Adverse Events

Adverse events will be coded according to the Medical Dictionary for Regulatory Activity (MedDRA) system dictionary.

CEC adjudicated data Tables to summarize the incidence rates will be created for each of the following groups: (At 1 year, 1- 2 years, and 2- 3 years)

- Adverse events (non-Serious) related to intervention (Procedure, anti-platelet therapy (APT)), Causal, Probable
- Serious adverse events related to Intervention (Procedure, APT)- Causal, Probable
- Adverse device effects (Non-SAE Related to Study Device- causal, probable)
- Serious adverse device effects (SAE Related to Study Device-causal, probable)
- Unanticipated serious adverse device effects (USADE)/UADE
- Adverse events by severity (Mild, Moderate and Severe) related to Device, Procedure or APT (causal, probable)

PR-NV16099

Version C

14. Ethics

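### Seven of the ten visit types with an adverse event instruction limit it to events 'of interest', in conflict with the all-AE rule of section 11, so unlisted, mainly non-serious events may be under-asked

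*Combined protocol and SAP*

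**What the plan says.** Two scopes appear in the protocol.

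**Narrow.** The pre-procedure list (9.4), the five scheduled follow-up lists (9.9.1 to 9.9.5) and the unscheduled-visit list (9.9.6) each contain the item "Assessment of Adverse events of interest". The glossary does not define the term. Section 10.1 opens its table with "Anticipated Adverse Events and Adverse Device Effects associated with use of the study device and the study procedure(s) include" and then groups the entries under four events-of-interest headings: neurological, procedural, device-related and antiplatelet-related. Section 12.1 cites 10.1 as the source of the pre-specified events of interest that the Clinical Events Committee (CEC) adjudicates.

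**Broad.** Section 11 states: "All adverse events (AEs) will be collected and evaluated from point of enrollment through study exit", and ties this to the schedule of assessments. The baseline list (9.2) has "Assessment of Adverse Events (Assess adverse events after informed consent is signed". The discharge list (9.7) has "Assessment of Adverse events", and the retreatment list (9.8) has the same item. Footnote 12 of Table 9-1 also speaks of adverse events without a qualifier.

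**Analysis.** Section 13.8.4 plans CEC-adjudicated tables for 1 year, 1 to 2 years and 2 to 3 years. They cover non-serious and serious events related to the intervention, non-serious and serious device effects, "Unanticipated serious adverse device effects (USADE)/UADE", and related events by severity.

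**The concern.** Study staff work from the visit lists. Someone who completes the 9.9 item as written asks about the listed events and has done what the list requires. The rule in 9.14 that a missed required assessment is a deviation would not clearly catch the difference. Someone who works from section 11 asks about everything. The two would record different data from the same patient.

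This is a single-arm study of an implant with changed wire construction, wire count and size range and a new resheathing mechanism. No control arm collects events in the same way, so a low rate of unlisted events could reflect either the device or the question asked. At stake is the completeness of the descriptive adverse event tables, mainly their non-serious part.

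**Working it through.** No arithmetic beyond a count applies. The check sets the passages side by side.

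**1. Adverse event item at each visit type**

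| Visit type | Section | Scope |
|---|---|---|
| Baseline | 9.2 | adverse events |
| Pre-procedure | 9.4 | of interest |
| Discharge | 9.7 | adverse events |
| Retreatment | 9.8 | adverse events |
| 30-day | 9.9.1 | of interest |
| 180-day | 9.9.2 | of interest |
| 1-year | 9.9.3 | of interest |
| 2-year | 9.9.4 | of interest |
| 3-year | 9.9.5 | of interest |
| Unscheduled | 9.9.6 | of interest |

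Narrow: 1 (pre-procedure) + 5 (scheduled follow-up) + 1 (unscheduled) = 7. Broad: 3. Total: 10.

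**2. One visit type contradicts itself.** Section 9.8 says "A retreatment will be considered an" unscheduled visit and then uses the broad item. Section 9.9.6, on unscheduled visits, uses the narrow one.

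**3. Does the schedule settle it?** Section 11 refers to the schedule of assessments, and 9.11 names Table 9-1 for methods and timing. The row that carries footnote 12 is ticked at every visit, and the footnote has no 'of interest' limit. This favours the broad reading. However, the footnote mark sits on the baseline cell, and the row label is not readable in the extracted text, so its exact wording could not be confirmed. The visit lists still say something narrower.

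**4. Which events depend on the visit item?**
- Serious events and unanticipated device effects: section 11.2 requires the investigator to notify the sponsor within 24 hours of becoming aware, whatever the visit.
- Device deficiencies: section 11.3 requires all of them to be reported.
- Primary safety endpoint: stroke and neurological death are on the 10.1 list, and the CEC adjudicates them.
- Non-serious events outside the 10.1 list: no expedited route applies, so assessment at visits is the main way to find them.

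**5. Which tables in 13.8.4 does the last group feed?** It feeds non-serious intervention-related events, non-serious device effects, and the severity breakdown of related events.

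**The case against.** A reader might infer that unanticipated device events are simply not elicited after discharge, and that the row for "Unanticipated serious adverse device effects (USADE)/UADE" is therefore biased toward zero. The documents do not support this, for four reasons.

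- Nothing restricts collection to events of interest or exempts other events. Section 11 binds every site through study exit.
- By the definitions in 11.1.5 and 11.1.6, these are serious effects or problems, and their reporting does not rest on the visit item.
- A listed event can itself be unanticipated if its severity or incidence is unexpected. The narrow item would elicit such an event.
- Baseline, discharge and retreatment already use the broad wording.

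There is more to say for the plan. The 10.1 list is wide, and its mechanical-failure entry is open-ended. Each follow-up visit also includes a neurological examination and a medication record, which can bring unlisted events to light. Apart from the row for unanticipated effects, the 13.8.4 tables hold only events judged causally or probably related, so missed unrelated events would not enter them. No comparison of adverse event rates between sites is planned, so the small average number of patients per site adds nothing to the point.

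All of this stands and narrows the finding, but it does not remove it. The 24-hour duty starts once the investigator knows of an event and does not tell anyone to ask. For a non-serious, unlisted event that is related to the device, procedure or antiplatelet therapy, two instructions in the same protocol still differ.

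**Conclusion.** The inconsistency is real and should be corrected. Seven of ten visit types, including every scheduled follow-up visit from 30 days to 3 years, carry wording narrower than the collection rule in section 11. The likely consequence is limited: unlisted, mainly non-serious related events may be under-asked, and the corresponding 13.8.4 tables may be incomplete and uneven across visits and sites. The size cannot be estimated, because the documents give no rate for such events and no indication of which instruction sites follow. The primary safety endpoint and the reporting of serious events, unanticipated device effects and device deficiencies are not affected.

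Two assumptions apply. First, 'of interest' is taken to mean the 10.1 list; this is inferred from the headings of 10.1 and the reference in 12.1, since no definition is given. Second, the adverse event row of Table 9-1 is taken to have no qualifier; if it has one, the conflict with section 11 reaches the schedule as well.

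**What to change.** - In 9.4 and 9.9.1 to 9.9.6, delete 'of interest', so that each list reads "Assessment of Adverse events", as 9.7 and 9.8 already do.
- Confirm that the adverse event row of Table 9-1 states the same scope.
- Keep the 10.1 list as the scope of events-of-interest adjudication under 12.1.

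Section 9.2.3, item 3, which ties new medications to events of interest, could be aligned at the same time. That is optional and not needed to resolve the conflict.

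The cost is two words deleted at seven visit types and some additional adverse event entries, all of which section 11 already requires.

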- 24. Subject has extradural target aneurysm <12mm which is not symptomatic or not exhibiting aneurysm growth (exception: unless it is a fusiform aneurysm <12 mm i.e., asymptomatic extradural fusiform aneurysms <12 mm can be included).
- 25. Any known contraindication to treatment with the Pipeline[™] Vantage Embolization Device with Shield Technology[™], or use of antiplatelet therapy including:
 - d. Active bacterial infection
 - e. Contraindication to DAPT agents
- 26. Pre-existing stent is in place in the parent artery at the target intracranial aneurysm location.
- 27. Platelet count < 100 x 10^3 cells/mm³ or known platelet dysfunction.
- 28. The Investigator determines that the health of the subject or the validity of the study outcomes (e.g., high risk of neurologic events, conditions that may increase the chance of stroke) may be compromised by the subject's enrollment.
- 29. Subject is pregnant or wishes to become pregnant during the first year of study participation.
- 30. Subject is participating in another clinical trial at any time during the duration of the study that could confound the treatment or outcomes of this investigation.
- 31. Subject with known allergy to platinum or cobalt chromium alloy (including the major elements platinum, cobalt, chromium, nickel or molybdenum).
- 32. History of previous acute ischemic stroke
- 33. Subject is unable to undergo DSA or CTA imaging at follow-up.

PR-NV16099

Version C

9. Study Procedures

Schedule of Events 9.1.

An overview of the assessments to be performed at each follow-up interval along with the required timing is provided in Table 9-1. Scheduled visits occurring outside of the specified date range will be considered clinical protocol deviations. After the clinical investigation has been completed, subjects will be followed according to standard of care.

Baseline	Baseline Procedure				Follow-up					
	Pre- (Day 0)	Post- (Day 0)	Day 1-7	30-day	180-day	1-year	2-year	3-year	Un- scheduled	
Time -7 to Window -30 days	Day 0	Day 0	1-7 days	±7 days	±30 days	± 56 days	± 56 days	± 56 days		
Х	х									
Х										
Х										
Х										
X1										
	X6					X6	X6	X6		
X ¹⁰										
X ¹⁰										
Π) X ¹⁰										
	X ⁷									
	х	х	х	х	х	х	х	х	х	
		•							X	
		•							X ⁴	
X ²	~	~			~	~		X ¹¹	X ⁴	
					X ¹¹		~	X ¹¹	X ⁴	
(S)	X ⁵		X ⁵	X2	X ⁵	X ⁵	X ⁵	X ⁵	X ^{5,8}	
-,	х					Х	Ì		X ⁸	
х			х	х	х	х	х	х	х	
X ¹²	х	х	х	Х	х	Х	х	Х	х	

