
Table 9-1. Visit and Assessment Schedule

[figure not shown]
⁹ DSA at pre-procedure to be used for final aneurysm measurements can be done any time prior to the index procedure

¹⁰ Can be done any time prior to the index procedure

¹¹If DSA not collected per standard of care, subject must undergo CTA imaging. For follow-up images after the 1-year follow-up, under certain conditions, MRA imaging may be obtained instead of a DSA or CTA imaging e.g., subjects with iodine allergies, borderline renal function, pregnancy, or concerns over excessive radiation. The justification for using MRA over DSA or CTA should be captured in the case report form. Precaution: DSA or CTA imaging are preferred over MRA imaging due to the risk of reduced image quality (artifact) when attempting to visualize near or inside the implanted device with MRA imaging. Note that MRA should not be used for any follow-up imaging within 1-year ¹²Assess adverse events after informed consent is signed.

Medtronic Controlled Information

PR-NV16099

An overview of the study procedures is shown in **Figure 9-1**

*As permitted by the IRB/REB, de-identified images taken per standard of care may be sent to the core lab for screening committee review prior to informed consent. Medtronic Controlled Information

This document is electronically controlled

3 Year Visit (±56 days)

Page 71 of 144

ŀ

PR-NV16099

Page 72 of 144

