9.4. Pre-Procedure Assessment

Subjects must undergo the device placement procedure within 30 calendar days of completion of all baseline assessment tests and procedures. On the day of the procedure and prior to treatment, the subject will again be evaluated and the following data shall be collected and recorded in the eCRF:

- Inclusion/exclusion criteria assessment
- Pregnancy test (Pregnancy test (serum or urine) only required for females of childbearing potential. Females who are surgically sterile or post-menopausal are not required to take a pregnancy test)
- Platelet count (can be done any time prior to the procedure)
- Platelet reactivity testing (If PRU is found below 60 or above 200 on the day of the procedure, the procedure should be delayed until it is within therapeutic range. In such cases, baseline measurements should be repeated if the next procedure is schedule >30 days from the initial planned procedure. If procedure is performed <30 days from the initial planned procedure. If procedure is performed <30 days from the initial planned procedure. If procedure is performed soldays from the initial planned procedure, the PRU measurements must be repeated but the other baseline measurements may be repeated per standard of care at the treating hospital). For OUS sites, a TEG test may be carried out instead of the PRU test (depending on PRU test availability). In cases where TEG test is carried out, the subject should have a pre-procedure therapeutic ADP% between >30% to <90%. If ADP% is <30% or >90% on the day of the procedure, the procedure should be delayed until it is within therapeutic range. In such cases, baseline measurements should be repeated if the next procedure is schedule >30 days from the initial baseline measurements. If procedure is performed <30 days from the initial baseline measurements must be repeated but the other baseline measurements may be repeated per standard of care at the treating hospital.
- Record protocol specified medications
- Record concomitant medications
- DSA imaging for final aneurysm measurements
- mRS assessment to be carried out by certified independent assessor at the site
- NIHSS
- Assessment of Adverse events of interest

PR-NV16099

Version C

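### The 180-day DSA or CTA has no required pregnancy test and no named alternative image in pregnancy; at 3 years the test precedes DSA but not the CTA that may replace it

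*Combined protocol and SAP*

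**What the plan says.** **180 days.** Section 9.9.2 requires "DSA imaging, if done per standard of care; if DSA not performed per standard of care, subject must undergo CTA imaging". The other listed assessments are medications, mRS, neurological examination and adverse events. No pregnancy test is listed, and the pregnancy-test rows of Table 9-1 and the synopsis schedule show no 180-day entry. Footnote 11 of Table 9-1 opens MRA only for later images: "For follow-up images after the 1-year follow-up, under certain conditions, MRA imaging may be obtained instead of a DSA or CTA imaging". It ends: "Note that MRA should not be used for any follow-up imaging within 1-year".

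**3 years.** Under 9.9.5, a subject whose aneurysm is occluded has DSA if that is standard of care; otherwise "if DSA not collected per standard of care, subject must undergo CTA imaging". The test has a narrower trigger: "At the 3-year follow-up, pregnancy test is only required for female subjects of childbearing potential that are undergoing DSA imaging". The same section provides: "Under certain conditions, MRA imaging may be obtained instead of a DSA or CTA imaging e.g., subjects with iodine allergies, borderline renal function, pregnancy". Concern about excessive radiation is also given as a reason for MRA.

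**Elsewhere.** On the procedure day, section 9.4 lists: "Pregnancy test (Pregnancy test (serum or urine) only required for females of childbearing potential". The 1-year visit (9.9.3) repeats the item. At 2 years (9.9.4) the test is required only before DSA, and no CTA is required there. Exclusion 29 bars entry if "Subject is pregnant or wishes to become pregnant during the first year of study participation". Section 9.14 treats any missed required assessment as a deviation and has deviations reported even when medically justified.

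**The concern.** The protocol evidently regards X-ray imaging of a pregnant woman as something to screen for. It tests on the procedure day, at the 1-year DSA, and before DSA at 2 and 3 years. The 180-day image uses the same modalities and has no such step. Exclusion 29 and the procedure-day test lower the risk in the first year, but neither detects a pregnancy that begins after the procedure.

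At 3 years the inconsistency is internal. Pregnancy is named as a reason to avoid CTA, yet the test that would reveal an unrecognised pregnancy is not required before CTA.

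At stake are a small safety margin for women of childbearing potential and a clear instruction to sites on what to do about the 180-day image in pregnancy. No statistical property of the trial depends on it.

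**Working it through.** The protocol states no figure on this point, so the first check sets the visits side by side.

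| Scheduled visit | Study image | Required pregnancy test |
|---|---|---|
| Baseline (9.2) | DSA, CTA or MRA | None listed |
| Pre-procedure (9.4) | DSA; footnote 9 lets it be done earlier | Yes, on the procedure day |
| 180 days (9.9.2) | DSA if standard of care, otherwise CTA | None |
| 1 year (9.9.3) | DSA | Yes |
| 2 years (9.9.4) | DSA if not occluded | Before DSA |
| 3 years (9.9.5) | DSA if not occluded; if occluded, DSA if standard of care, otherwise CTA | Before DSA only |

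Among the follow-up rows, two paths lead to a required X-ray image without a required test: 180 days by either modality, and 3 years by CTA. Tying the test to DSA is coherent at 2 years, where no CTA is mandated. It is not coherent at 3 years.

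The second check is size. The documents give neither the number of women of childbearing potential nor the share imaged by CTA, so these are assumptions:

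- Women of childbearing potential among 100 treated subjects: n = 10 to 25.
- Unplanned pregnancy rate: a = 2% to 6% per year.
- Time for which a pregnancy goes unrecognised: 6 weeks.
- Share imaged by CTA: c = 20% to 80%.

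One input comes from the documents. The occluded share is o = 75.0% (141/188, SHIELD OUS, 4.2.7) to 86.8% (79/91, PUFs, 4.2.2), both at 1 year and used here as a proxy for the 3-year branch.

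The chance that a given woman has an unrecognised pregnancy at a visit is p = a × 6/52.

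- Low: 0.02 × 6/52 = 0.00231.
- High: 0.06 × 6/52 = 0.00692.

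The expected number imaged is n × (per-woman probability). The chance of at least one is 1 − (1 − per-woman probability)^n.

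| Path | Per-woman probability | Expected, low | Expected, high | Chance of at least one |
|---|---|---|---|---|
| 180 days, DSA or CTA | p | 10 × 0.00231 = 0.023 | 25 × 0.00692 = 0.173 | 2% to 16% |
| 180 days, CTA only | p × c | 0.023 × 0.2 = 0.005 | 0.173 × 0.8 = 0.14 | 0.5% to 13% |
| 3 years, CTA, occluded | p × c × o | 0.023 × 0.2 × 0.75 = 0.003 | 0.173 × 0.8 × 0.868 = 0.12 | 0.3% to 11% |

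Each end of a range takes all inputs at their low or high values together. Exclusion 29 covers only the first year, so the 3-year pregnancy rate could be higher than assumed.

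The extra tests are 10 to 25 at 180 days. At 3 years they are n × o × c, from 10 × 0.75 × 0.2 = 1.5 to 25 × 0.868 × 0.8 = 17.4.

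**The case against.** The strongest reply is that the gap is tiny and partly covered.

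- **MRA at 3 years.** It may replace CTA for a known pregnancy or for radiation concerns, so a suspected pregnancy can also be handled without a test. This stands, and it limits the 3-year gap to pregnancy nobody has recognised.
- **Possible regulatory origin.** The version history records a clarification of pregnancy testing at 2 and 3 years, and ties revisions of the 180-day imaging to FDA comments. Linking the test to DSA may therefore be deliberate. Those comments are not reproduced, and the proposed change leaves the imaging and the advice against MRA before 1 year as they are.
- **Local practice.** Radiology departments may test in any case, and the imaging protocol given to sites (12.2) or the consent form may say so. Neither was available to check. That limits any claim about practice, but the written schedule is still incomplete, and the protocol did not leave testing to local practice at its other follow-up X-ray visits.

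A reader might go further in three ways that the documents do not support.

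- **That these are the only scheduled X-ray images without a prior required test.** Baseline imaging may be DSA or CTA, and 9.2 lists no test. A pre-procedure DSA done early under footnote 9 can also precede the procedure-day test. The point is confined to follow-up visits.
- **That a woman known to be pregnant at 180 days has no permitted route at all.** Section 9.15 allows withdrawal for safety, and 9.15.2 lets the investigator discontinue a subject for her well-being. These routes are blunt, since they end participation over one image, but they are stated.
- **That sites are compelled to image her, or penalised if they do not.** Nothing compels it. Section 9.14 logs medically justified departures along with the rest, and site restrictions are tied to persistent deviations.

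**Conclusion.** The point holds as a minor schedule correction. The protocol requires a 180-day DSA or CTA without the pregnancy test it uses at its other follow-up X-ray visits, and it names no alternative image for a woman known to be pregnant then. At 3 years it leaves the mandatory CTA outside the test requirement, which matters only for unrecognised pregnancy.

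The number of pregnancies expected to be imaged unrecognised is well below one on every path: at most about 0.17 at 180 days and 0.12 at 3 years. All inputs except the occlusion range are assumed. These figures count pregnancies imaged, not harm. The documents do not show how often the CTA would exceed local routine care, so no added radiation exposure is claimed. Endpoints, power and error rates are untouched.

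**What to change.** 1. Add the existing serum or urine test for women of childbearing potential to the 180-day visit, in 9.9.2 and in both schedules (synopsis and Table 9-1).
2. In 9.9.5 and the matching Table 9-1 footnote, extend the 3-year condition for the test from DSA alone to DSA or CTA.
3. State that after a positive 180-day test the study image is deferred or omitted and the reason recorded. No exemption from 9.14 is needed, and MRA before 1 year need not be reintroduced.

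The cost is about 10 to 25 tests at 180 days and 2 to 17 at 3 years under the same assumptions, all at visits already scheduled. It also needs a protocol amendment; if that is judged significant, 15.8 requires a justification and regulatory and IRB/REB approval. Rarely, a 180-day image will be missing, but it is not the 1-year image on which the primary effectiveness endpoint rests.
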